1. STUDY OBJECTIVES

This clinical trial studies autologous cell therapies in subjects with cerebral palsy (CP). We aim to compare the effects of two specific autologous cell therapies - bone marrow derived mononuclear cells (BMMNCs) versus human umbilical cord blood cells (hUCBs). Although both cellular products have an established safety record in children in the setting of bone marrow transplantation as well as a more limited experience with traumatic brain injury, the safety of these cellular therapies in subjects with CP will be evaluated in this study. This study will examine the following broad aims:

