3. STUDY DESIGN

This is a randomized, blinded, placebo-controlled, cross-over study designed to treat CP in pediatric subjects with an IV infusion of autologous bone marrow mononuclear cells or autologous umbilical cord blood cells. A total of 30 subjects (15/arm) will be enrolled into the study. Subjects will be randomized 2:1 (treatment: sham). All subjects will return for follow-up at 6 months, 12 months, and 24 months post-treatment. At the 12 months post-treatment visit, those subjects who originally received the sham will be offered the BMMNC or hUCB treatment (Figure 1).

Figure 1.

Thirty subjects will provide a preliminary assessment of potential SAEs with a 10 to 15% incidence that we would be able to detect with reasonable confidence. The sample size would also allow us to acquire point estimates of different events that we would use for a larger efficacy study. The sample size determination is based on the historical treatment effect size of 15% decrease in gray and white matter volumes. Preservation

of this volume is based on the Phase 1 pediatric acute treatment of severe TBI using autologous bone marrow derived mononuclear cells as compared to historical control volumetric analyses by Wilde et al. (Wilde, E, et. al. 2005; Cox, C et al., 2011.)

Drug/Biologic: A single dose of intravenously administered autologous BMMNC or hUCB. The BMMNC dose will be 6X10⁶ cells/kg body weight infused over 15 minutes at a 1 million cells/ml concentration. For the hUCB arm, the minimum acceptable dose will be 2X10⁶cells/kg body weight based on rodent data (Lu, 2001), and the maximum allowable dose will be 10X10⁶cells/kg. The target dose will be the maximum available dose within this range. The bone marrow harvest, the hUCB reanimation, cell processing and product infusion will occur at Children's Memorial Hermann Hospital and the Griffin Stem Cell Laboratory.

Placebo: 0.9% saline will be infused in an identical syringe over the same rate as if receiving a cell infusion, (See "Blinding of Placebo Infusion").

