5. STUDY INTERVENTIONS

5.1 Bone Marrow Arm

5.1.1 Subject Recruitment

Fifteen pediatric subjects without banked umbilical cord blood meeting eligibility criteria will be enrolled into the bone marrow arm of the study. The parent(s)/LAR of potential subjects will contact the research team at The University of Texas Health Science Center at Houston. During this telephone call, an overview of the study and basic eligibility requirements will be reviewed. If eligibility requirements are met and the parent(s)/LAR willing to participate, instructions will be provided on forwarding medical records to the research team for review and a consent and authorization for release of information (for contact with the subjects primary care provider [PCP]) will be sent to the parent(s)/LAR. After receipt of medical records and contact with the PCP (if indicated) a telephone conference call will be scheduled with the parent(s)/LAR. During the call, study procedures and the informed consent document will be reviewed. Time will be given to answer questions. The parent(s)/LAR will not be pressured to make a decision on participation during the call. Parent(s)/LAR choosing to participate in the study will be asked to return the signed informed consent in the postage paid envelope provided.

After receipt of the signed informed consent document, the parent(s)/LAR will be contacted by the research team to schedule the baseline/treatment visit. The parent(s)/LAR will be responsible for making all travel arrangements.

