5.1.2 Randomization

The randomization sequence will be computer-generated. The subject will be assigned to the treatment or control arm in a 2:1 ratio using sequentially numbered, opaque, sealed envelopes prepared by a member of the Center for Surgical Trials and Evidence-based Practice (C-STEP) not involved in the clinical trial.

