5.2.3 Subject Recruitment

Fifteen pediatric subjects who have their umbilical cord blood banked with CBR and meet study criteria will be enrolled into the cord blood study arm. The parent(s)/LAR of potential subjects will contact CBR. After receiving permission to release the subject's contact information, CBR will then relay the contact information to the research team, who will then contact the parent(s). During this telephone call, an overview of the study and basic eligibility requirements will be reviewed. If eligibility requirements are met and the parent(s)/LAR willing to participate, instructions will be provided on forwarding medical records to the research team for review and a consent and authorization for release of information (for contact with the subjects primary care provider [PCP]) will be sent to the parent(s)/LAR. After receipt of medical records and contact with the PCP (if

indicated) a telephone conference call will be scheduled with the parent(s)/LAR. During the call, study procedures and the informed consent document will be reviewed. Time will be given to answer questions. The parent(s)/LAR will not be pressured to make a decision on participation during the call. Families choosing to participate in the study will be asked to return the signed informed consent in the postage paid envelope provided.

After receipt of the signed informed consent document, CBR will be notified to release cord blood information to the research team. The parent(s)/LAR will be contacted by the research team to schedule the baseline/treatment visit. The parent(s)/LAR will be responsible for making their travel arrangements.

Approximately 4 – 6 weeks prior to the scheduled procedure date, the subject will have the infectious disease testing for HIV 1 and II, Hepatitis B and C, HTLV 1 and II, Syphilis, CMV, and West Nile Virus. An additional 8 – 10 mL of blood will be collected at this time and shipped overnight to a Cell and Gene Therapy (CAGT) lab in Houston for HLA testing. All lab results will be sent to the research team for review prior to the baseline/treatment visit. If the subject has a positive HIV, Hepatitis B, or C test; they will be excluded from the study.

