5.2.5 Randomization

Subjects in the hUCB group will be randomized after receipt of subject and maternal infectious disease results and CBR cord blood information on viability and cell count.

Subjects found ineligible for cord blood infusion due to low or non-viable cell count or contamination will be offered the opportunity to enroll in the other treatment arm of the study if the enrollment limit for the BMMNC group has not already been met. The randomization sequence will be computer-generated. The subject will be assigned to the treatment or control arm in a 2:1 ratio using sequentially numbered, opaque, sealed envelopes prepared by a member of the Center for Surgical Trials and Evidence-based Practice (C-STEP) not involved in the clinical trial.

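### Section 1 aims to compare BMMNC with hUCB, but product is not randomised and no specified model contains a product term

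*Combined protocol and SAP*

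**What the plan says.** The introduction to Section 1 states "We aim to compare the effects of two specific autologous cell therapies" and sets BMMNC against hUCB. The numbered objectives that follow ask something else: 1.1 whether either product is safe, and 1.2 whether outcomes after autologous cells are better than in controls.

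Product is decided at recruitment. Section 5.1.1: "Fifteen pediatric subjects without banked umbilical cord blood meeting eligibility criteria will be enrolled into the bone marrow arm". Section 5.2.3 takes "Fifteen pediatric subjects who have their umbilical cord blood banked with CBR". Under Section 5.2.5, children whose cord unit has a low or non-viable count or is contaminated "will be offered the opportunity to enroll in the other treatment arm of the study" if marrow places remain.

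Randomisation comes after that and concerns only cells or sham. Section 5.1.2: "The subject will be assigned to the treatment or control arm in a 2:1 ratio". Section 5.2.5 gives the same ratio for the cord arm: "Subjects in the hUCB group will be randomized after receipt of subject and maternal infectious disease results", and after the bank's data on the unit. Section 3 fixes the size: "A total of 30 subjects (15/arm) will be enrolled into the study".

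**The concern.** A sentence that opens the objectives and sets one product against the other reads as a question the trial will answer. Nothing in the protocol marks it as descriptive. Product is inseparable from the kind of family enrolled and from how the child is handled, so a raw difference between the two treated groups would mix all of these.

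Section 9.1.1 leaves evaluation exploratory, takes p = 0.05 as significant and makes no multiplicity adjustment. Nothing there prevents an unlabelled product p-value from being reported against the stated aim. A separate consequence is that the pooled treatment-versus-control models ignore the two sources within which children are recruited and randomised.

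**Working it through.** **1. What differs along with product**

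| | Bone marrow arm | Cord blood arm |
|---|---|---|
| Entry | No banked cord blood, or an unusable unit (5.1.1, 5.2.5) | Cord blood held by one private bank (5.2.3) |
| First contact | Family to research team (5.1.1) | Family to bank, which passes details on (5.2.3) |
| Procedure | Sedated harvest or sham harvest, then infusion (5.1.3, 5.1.4) | Infusion with no harvest (5.2.7) |
| Dose rule | Single target per kg (3, 5.1.6) | Largest available within a range per kg (3) |
| Placebo medium | Saline with albumin (5.1.9) | Dextran 40 with albumin (5.2.7) |
| Randomised | Cells v sham, 2:1 (5.1.2) | Cells v sham, 2:1 (5.2.5) |

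The switch in Section 5.2.5 depends on unit quality and free places. It weakens the link between banking and product but is not random.

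**2. Where product appears in the analysis**

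- Section 9.1.2, imaging model: the group factor has two levels, treatment and control.
- Section 9.1.2, brain-behaviour model: the same two levels, with MRI/DTI variables.
- Section 9.1.2, comparability check: demographics, with socioeconomic status as an example, for groups which that section defines as treatment and control.
- Section 6.4.9: with versus without treatment, using either product.
- Section 6.4.2: with and without BMMNC; hUCB is not named.

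None contains a product term.

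**3. The plan's own sample size**

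Section 3 supports 30 children by SAEs of 10 to 15% incidence and by a 15% volume effect. The chance of at least one event is 1 − (1 − p)^n. For n = 30 it is 1 − 0.90^30 = 95.8% and 1 − 0.85^30 = 99.2%. This can only be set beside the plan, not matched to it, because the confidence sought is not quantified. The volume basis has no SD or power. Neither basis concerns a difference between products.

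**4. Size of a product contrast, for scale**

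Inputs: 15 per source (Section 3). At 2:1 this gives about 15 × 2/3 = 10 treated and 15 × 1/3 = 5 sham. Two-sided 0.05 follows from Section 9.1.1; 80% power is assumed. The plan gives no between-product effect or SD, so results are in SD units. Smallest detectable difference, normal approximation: (1.960 + 0.842) × √(sum of 1/n).

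- Treated 10 v 10: 2.802 × √(1/10 + 1/10) = 1.25 SD; 1.32 SD by noncentral t. Power by t is 9% at 0.3 SD, 18% at 0.5, 40% at 0.8 and 56% at 1.0.
- Treated 15 v 15, if every sham child crosses over: 2.802 × √(2/15) = 1.02 SD; 1.06 SD by noncentral t. The added children are treated about a year later, after the blind is broken (5.1.8, 5.2.10).
- Product-by-treatment, each product against its own sham: 2.802 × √(1/10 + 1/5 + 1/10 + 1/5) = 2.17 SD.
- Needed per product for 80% power, 2 × 2.802²/d²: 63 at 0.5 SD and 25 at 0.8 SD.
- A binary event at 10 v 10, Fisher's test: at least 5 events against 0 for p ≤ 0.05. Power is 0.4% for 10% v 15% and 15% for 10% v 40%.

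**The case against.** The strongest reply is that the sentence is introductory. No endpoint, hypothesis, sample-size statement or test depends on it, and the absence of a product term can be read as evidence that no head-to-head test is planned. That stands, and it limits the point to a mismatch between a stated aim and the design.

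Comparing effects also need not mean a randomised superiority test. Section 9.1.1 reports estimates with 95% confidence intervals, and Section 3 wants point estimates for a larger study, so a side-by-side description by product is feasible. That stands too. A reader might infer that the products cannot be compared in any form; the documents do not support this.

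Nor is it right to infer that confounding by banking status is beyond remedy. Each source has its own concurrent randomised sham, so contrasting the two within-source effects avoids baseline prognostic confounding. It leaves effect modification and procedural differences, and it is very imprecise (about 2.2 SD).

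Finally, 1.32 SD might be read as the power of a planned analysis. It is not: the plan specifies no such test, and the figure depends on how many sham children cross over.

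A source term is also a change of analysis and not only of wording. That is fair, and its cost is stated below.

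**Conclusion.** The concern holds in a limited form. Section 1 states a product comparison that the design does not deliver. Product is set mainly by banking status and unit usability, it is bundled with recruitment, procedure and placebo medium, and no specified model contains it. There is thus no unconfounded or prespecified comparison of BMMNC with hUCB.

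The detectable differences run from 1.06 SD to about 2.2 SD depending on the contrast. They assume 80% power, an exact 2:1 split and no dropout, and they describe precision only; they say nothing about bias.

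A reader might go further and infer that the trial fails its objectives. The documents do not support that: objectives 1.1 and 1.2 do not need the product contrast, and the randomised comparison of cells with sham is untouched.

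**What to change.** 1. In Section 1, restate the aim as each product versus its own concurrent sham, and pooled cells versus sham.
2. In Section 9, state that any BMMNC v hUCB contrast is non-randomised and descriptive, given as estimates with 95% confidence intervals and not read as a test of product superiority.
3. In Section 9.1.2, include cell source as a stratification factor in the pooled treatment-versus-control models, because randomisation is done within source.

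Items 1 and 2 cost only wording. Item 3 costs about one degree of freedom per model: with 30 children and two groups, the between-subject residual goes from 30 − 2 = 28 to 30 − 3 = 27 before other covariates. No new data or visits are needed.

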1.1 Primary Objective

To determine if autologous cells using either BMMNCs or hUCBs are safe to administer in children with CP.

Primary safety outcome measures:

- 1. In-hospital infusion toxicity: pulmonary and hepatic function; new seizures, hemorrhagic lesions or ischemic lesions on imaging.
- 2. Long-term safety: development of new mass lesions or other pathological structural changes; worsening neurological status.

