6. CLINICAL AND LABORARTORY EVALUATIONS

- 6.1 Schedule of Events (See Appendix A)
- 6.2 Infusion Toxicity Complications
- 6.2.1 Hemodynamic Instability

Subjects will be admitted to the pediatric at Children's Memorial Hermann Hospital following the baseline outpatient visit and will be monitored continuously until discharge as described in previous sections. A primary concern is the precipitation of hemodynamic instability associated with infusion-related toxicities of cellular product transplant. It has been reported that hypotension, hypertension and bradycardia can occur from transplantation of cellular product that has been cryopreserved in dimethylsulfoxide (DMSO) and RBC depletion. To minimize the effect of these, our hUCB product will be washed according to Standard Operating Procedures prior to

infusion. However, it is possible that some quantity of DMSO will remain. To minimize the risk of hemodynamic instability, maintenance + an additional 10 – 40mL/Kg intravenous 0.9% saline volume replacement will occur concomitantly with the cellular product infusion. Blood pressure elevation will be defined as an increment of more than 20% from the baseline value at the beginning of the infusion (Konuma, 2008). An adverse event will be defined as a sustained (> 10 minutes) >20% decrease in MAP. Transient decreases in the mean arterial pressure (MAP) that respond to fluid infusion or inotropes will not be considered adverse events. Prolongation of capillary refill greater than 2 seconds from baseline as well as a greater than 20% change in heart rate during the procedure will prompt an evaluation as to the etiology of the change in hemodynamic status. Bradycardia, defined by a sustained reduction in heart rate, less than 40beats/min, that is unresponsive to intravenous fluid or inotrope support will be considered an adverse event. Restoration of hemodynamics to baseline will allow resumption of infusion. Inability to transfuse will preclude further participation in the study, though the subject will be followed for data collection per protocol.

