6.2.4 Renal Complications

DMSO induces hemolysis of contaminating red blood cells during the hUCB storage and may also induce in vivo hemolysis and ultimately pigment nephropathy (Smith, 1987). To minimize the effect of these, our hUCB product will be washed according to Standard Operating Procedures prior to infusion. Though unlikely, it is possible that some quantity of DMSO will remain which could cause toxicity. Renal function/events corresponding to the CTCAE v4.0 Grade 3 will trigger the stopping rules.

IRB NUMBER: HSC-MS-12-0876
UTHeath
The University of Texas
The University of Texas

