7. MANAGEMENT OF ADVERSE EXPERIENCES

There are currently no neuroprotective/restorative treatments for CP in adults or children. Any potential risks must be weighed against the lack of treatment alternatives.

The majority of the risk related to the study is associated with the bone marrow harvest and infusion periods and are discussed in section 6.2.

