9. STATISTICAL CONSIDERATIONS

9.1 Outcomes

9.1.1 Primary Safety Objective

Baseline characteristics of participants will be summarized using descriptive statistics and tabulations. Evaluation of data will be guided by exploratory analyses. All results will be reported as point estimates (percentages for binary outcomes and means \pm SD and median (range) for continuous outcomes) with corresponding interval estimates (two-sided 95% confidence intervals). No adjustments for multiple comparisons will be made and a p-value of 0.05 will be considered statistically significant.

These data are collected over time and will be longitudinal in nature with several predefined points of follow-up. We will use analytic strategies and methods applicable to such designs. For each participant in the cohort we have a set of "k" independent variables $\mathbf{x}' = (x_1, x_2, ..., x_k)$, of which some may be time varying (e.g., blood pressure) and others do not change over time (e.g., gender). In addition, the outcome variables of interest are also measured repeatedly over time (e.g., temperature, signs of infection, neurological exams, CBC, chem-20). We plan to explore any changes over time between hospital discharge and long-term follow-up at 6 months, 1 year, and 2 years after cell treatment with repeated measure model analyses. In this study, we plan to explore and identify potential factors associated with time to SAEs, AEs, death (refer to section 6.2), loss to follow-up (short term and long term), and improvements in functional outcomes (refer to section 6.3). We plan to explore the factors associated with the time to an event using survival analysis methods which incorporate information about the timing of withdrawals, deaths, and functional improvements (if any) of subjects during the follow up period. We plan to first use descriptive statistics to explore the characteristics of the subjects among events and then will use the Kaplan-Meier method to estimate the time to an event. Combined, these secondary analyses may provide useful preliminary estimates for the design of future cell studies.

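### The primary in-hospital infusion-toxicity outcome in 1.1 omits the hemodynamic, renal and harvest events that the protocol describes elsewhere, and no section says that blood pressure elevation is counted

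*Combined protocol and SAP*

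**What the plan says.** Section 1.1 gives two primary safety outcomes. The in-hospital one is "In-hospital infusion toxicity: pulmonary and hepatic function; new seizures, hemorrhagic lesions or ischemic lesions on imaging". The other is "Long-term safety: development of new mass lesions or other pathological structural changes; worsening neurological status".

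Section 6.2, on infusion toxicity, has five parts: hemodynamic, pulmonary, hepatic, renal and neurologic. Of the first, 6.2.1 says: "A primary concern is the precipitation of hemodynamic instability associated with infusion-related toxicities of cellular product transplant". It gives two rules on blood pressure. For falls: "An adverse event will be defined as a sustained (> 10 minutes) >20% decrease in MAP". For rises: "Blood pressure elevation will be defined as an increment of more than 20% from the baseline value". Only the first is called an adverse event. On the kidney, 6.2.4 says: "Renal function/events corresponding to the CTCAE v4.0 Grade 3 will trigger the stopping rules". Sections 5.1.7 and 5.2.9 list hemodynamics, and renal indices alongside pulmonary and hepatic ones, as post-infusion monitoring. Section 7 states: "The majority of the risk related to the study is associated with the bone marrow harvest and infusion periods", and 7.2 names hemorrhage, nerve injury and fracture as harvest complications.

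Section 9.1.1, headed as the primary safety objective, describes independent variables "of which some may be time varying (e.g., blood pressure) and others do not change over time (e.g., gender". Its examples of repeatedly measured outcomes are temperature, signs of infection, neurological exams, CBC and chem-20. It plans time-to-event analyses of AEs, SAEs and death with a reference to 6.2, and it calls these analyses secondary.

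**The concern.** An outcome named as infusion toxicity should cover what the same protocol calls infusion toxicity. Here it leaves out the item that 6.2.1 singles out as a primary concern, and the renal indices that 5.1.7 and 5.2.9 place beside the pulmonary and hepatic ones. Section 7 refers the reader to 6.2 for harvest risk, but 6.2 has no harvest part, so harvest events have no place in the primary outcome or in the toxicity definitions.

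At stake is what the primary safety result covers. A report that follows 1.1 could present it without a hemodynamic, renal or harvest row. A hypertensive response to infusion could be recorded as vital signs and appear in no named safety outcome. If post-infusion blood pressure were also used as a covariate, as the example in 9.1.1 permits, part of any infusion effect on another outcome would be adjusted away.

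**Working it through.** **Step 1. Set the lists side by side.**

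| Event type | Described in | In 1.1? | Other route into the analysis (9.1.1) |
|---|---|---|---|
| Pulmonary | 6.2.2, 5.1.7, 5.2.9 | Yes | AEs |
| Hepatic | 6.2.3, 5.1.7, 5.2.9 | Yes | AEs, chem-20 |
| Neurologic | 6.2.5 | Yes (seizures, lesions, worsening status) | AEs, neurological exams |
| Hemodynamic | 6.2.1, 5.1.7, 5.2.9 | No | AEs as defined in 6.2.1; blood pressure only as an independent variable |
| Renal | 6.2.4, 5.1.7, 5.2.9 | No | AEs; probably chem-20 (assumption) |
| Harvest | 7, 7.2 | No | AEs only |
| Infection | 7.1 | No | Named as an outcome variable |

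Two of the five organ systems in 6.2 are absent from 1.1, and so are harvest events.

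**Step 2. See what the adverse-event route carries.** A fall in mean arterial pressure of more than 20% that lasts over 10 minutes is an AE. A short-lived fall corrected by fluids or inotropes is expressly not one. Bradycardia counts only below 40 beats/min and when unresponsive to support. Blood pressure elevation has a threshold but no status. Under 10.7 an abnormal value becomes an AE on the investigator's judgement of clinical significance or temporal relation. Elevation can therefore enter case by case, but no rule brings it in.

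**Step 3. See what the modelling route carries.** The repeated-measures analysis in 9.1.1 starts at hospital discharge, after the in-hospital period that the first primary outcome concerns.

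**Step 4. Numbers at risk.** Section 3 gives 30 subjects, 15 per arm, randomised 2:1. That is 15 × 2/3 = 10 cells and 5 sham per arm, or 20 and 10 overall before crossover, if the ratio is met exactly. Only the bone marrow arm has a harvest or sham harvest (5.1.3, 5.1.4), so harvest events have 10 v 5 at risk.

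**Step 5. The plan's own figure.** Section 3 says 30 subjects can detect SAEs of 10 to 15% incidence with reasonable confidence, and gives no confidence level. The chance of at least one event is 1 − (1 − p)^n:

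- n = 30: 1 − 0.90^30 = 95.8%; 1 − 0.85^30 = 99.2%
- n = 20: 1 − 0.90^20 = 87.8%; 1 − 0.85^20 = 96.1%
- n = 10: 1 − 0.90^10 = 65.1%; 1 − 0.85^10 = 80.3%

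The claim fits a 95% level for all 30 pooled, but only 20 receive cells before crossover. At the top of the 0.1–0.4% serious harvest complication rate quoted in 7.1, 10 harvests give 1 − 0.996^10 = 3.9%.

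**Step 6. What a row with no events would say.** The exact two-sided 95% upper limit for 0 of n is 1 − 0.025^(1/n):

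- n = 20: 1 − 0.8316 = 16.8%
- n = 10: 1 − 0.6915 = 30.8%
- n = 5: 1 − 0.4782 = 52.2%

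These limits do not measure the gap in 1.1 and apply equally to items already listed. They show how little an empty or missing row establishes at this size.

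**The case against.** The strongest reply is that nothing is lost. Adverse experiences are collected from randomization (10.7) and graded by CTCAE (10.7.1). Hemodynamics and renal indices are monitored in both arms. The medical safety monitor reviews safety data in real time (10.6.1), and the last stopping rule in 10.8.1 covers any Grade 4–5 event judged temporally related. Section 9.1.1 analyses AEs with reference to 6.2. No test or pass/fail rule rests on the list in 1.1, so which items are labelled primary is arguably the sponsor's choice.

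Much of this stands, and it rules out several stronger readings that a reader might infer:

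- **That the trial would miss these toxicities.** It would not. They are collected and monitored, and a sustained fall in pressure is already an AE.
- **That infection is left out.** Signs of infection and temperature are outcome variables in 9.1.1.
- **That the safety models adjust for post-infusion blood pressure.** The wording in 9.1.1 is an example. It commits no model to that adjustment and does not bar blood pressure from being an outcome.
- **That every omitted category is a main risk.** Residual DMSO toxicity is called unlikely in 6.2.4, and the harvest complications in 7.1 and 7.2 are given as rare. Only hemodynamic instability is called a primary concern. Section 7 speaks of harvest and infusion periods together, and part of the infusion risk is in 1.1.

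The reply does not explain why an outcome named infusion toxicity differs from the protocol's own section on infusion toxicity. It also does not show where blood pressure elevation is counted. Monitoring and stopping rules protect subjects, but they do not determine what is reported as the primary result.

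**Conclusion.** The concern holds as a mismatch of definition. The formal primary in-hospital outcome does not include hemodynamic, renal or harvest events. They reach the analysis mainly as AEs, in analyses called secondary. Blood pressure elevation is defined but not assigned to any outcome, and 9.1.1 names blood pressure only as an independent variable.

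The size is two of five organ systems plus harvest events. Sample size, alpha and power do not change, and the documents state no power for the primary outcome. The limits of 16.8% (0 of 20) and 30.8% (0 of 10) assume full enrolment and an exact 2:1 split in each arm. That chem-20 carries the renal indices is also an assumption. The documents do not support the conclusion that the trial would overlook these events. This should be corrected, but it does not undermine the design.

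**What to change.** - **Section 1.1.** Add to the in-hospital/early primary outcome: hemodynamic events (the AEs in 6.2.1 plus blood pressure elevation by its existing definition of more than 20%), renal function and, for the bone marrow arm, harvest-site events.
- **Section 9.1.1.** List post-infusion blood pressure among the outcomes and allow only pre-infusion values as a covariate. State which safety variables are primary. Infection is already an outcome there and needs only a consistent label.
- **Tables.** Show each component by randomised group before crossover with exact (Clopper-Pearson) 95% limits, using the subjects at risk: 20 cells v 10 sham for infusion events, also by product (10 v 5 each), and 10 v 5 in the bone marrow arm only for harvest events. Using 20 v 10 for harvest events would dilute the rates with 15 children who had no such procedure.
- **Separately.** Section 6.2.4 says that Grade 3 renal events trigger the stopping rules, while 10.8.1 has no renal item and its general rule covers Grade 4–5 only. The two passages must be reconciled.

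The outcome and table changes cost wording in 1.1 and 9.1.1 and some table rows. The data are already monitored and recorded. The downside is a longer primary safety table that may look less favourable.
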